13.1 Ethical Standard

The investigator will ensure that this study is conducted in full conformity with the principles set forth in The Belmont Report: Ethical Principles and Guidelines for the Protection of Human Study participants of Research, as drafted by the US National Commission for the Protection of Human Study participants of Biomedical and Behavioral Research (April 18, 1979) and codified in 45 CFR Part 46; 62 Federal Regulations 25691 (1997) and the Declaration of Helsinki and Good Clinical Practice (GCP).

13.2 Institutional Review Board

The TEA device is similar to a TENS unit which is a non-significant risk but is not approved by the FDA.

As the device is not approved by the FDA the study team will have it reviewed by the Clinical Engineering Department for them to check into the safety. I have the device now. It is similar to a TENS device (non-significant risk) but not FDA approved.

The study will be reviewed for IRB approval. The study will not begin until IRB approval is granted.

13.3 Informed Consent Process

Informed consent is a process that is initiated prior to the individual's agreeing to participate in the study and continues throughout the individual's study participation. Extensive discussion of risks and possible benefits of this therapy will be provided to the study participants and their families. Consent forms (written in non-technical language) describing in detail the study interventions/products, study procedures, and risks are given to the study participant and written documentation of informed consent is required prior to starting intervention/administering study product. Consent forms will be IRB-approved and the study participant will be asked to read and review the document. Upon reviewing the document, the study team member will explain the research study to the study participant and answer any questions that may arise. The study participant will sign the informed consent document prior to any procedures being done specifically for the study. The study participants should have the opportunity to discuss the study with their surrogates or think about it prior to agreeing to participate. The study participants may withdraw consent at any time throughout the course of the trial. A copy of the informed consent document will be given to the study participants for their records. The rights and welfare of the study participants will be protected by emphasizing to them that the quality of their medical care will not be adversely affected if they decline to participate in this study.

13.4 Exclusion of Women, Minorities, and Children (Special Populations)

This study will exclude women who are pregnant. This is for their safety and the safety of their fetus(es).

The study also excludes children. This is because the population being studied are adults with IBS-C.

13.5 Study Participant Confidentiality

Study participant confidentiality is strictly held in trust by the participating investigators, their staff, and the sponsor(s) and their agents. This confidentiality is extended to cover testing of biological samples and genetic tests in addition to the clinical information relating to participating study participants.

The study protocol, documentation, data, and all other information generated will be held in strict confidence.

Any data, specimens, forms, reports, video recordings, and other records that leave the site will be de-identified of any protected health information (PHI) and replaced with study identifier to maintain study participant confidentiality. Information will not be released without written permission of the participant , except as necessary for monitoring by IRB, the FDA, OHRP and/or any other government officials, safety monitors/committees that may need the information to make sure that the study is done in a safe and proper manner, learn more about side effects, and/or analyze the results of the study.

13.6 Study Discontinuation

In the event that the study is discontinued:

- The study participants will not be able to continue with TEA.
- The study will not compensate study participants for incomplete visits.

14 Data Handling and Record Keeping

The investigator is responsible to ensure the accuracy, completeness, legibility, and timeliness of the data reported. All source documents should be completed in a neat, legible manner to ensure accurate interpretation of data. Dark ink is required to ensure clarity of reproduced copies. When making changes or corrections, cross out the original entry with a single line, and initial and date the change. DO NOT ERASE, OVERWRITE, OR USE CORRECTION FLUID OR TAPE ON THE ORIGINAL.

14.1 Data Management Responsibilities

The study coordinator will be responsible for data collection and management. The study coordinator will use the CRFs to document study participant visit. They will also review data for completeness prior to signing the bottom of the CRF. Periodically, every six months, the primary investigator or co-investigators will review the CRFs and for completeness. The barostat measurements will be saved as part of the research file by the GI physiology lab staff at the end of each visit.

14.2 Types of Data

Data for this study will include safety, barostat measurements, and survey results.

14.3 Timing/Reports

The primary investigator will review the study documents with the study coordinator every six months.

14.4 Study Records Retention

Study documents should be retained for a minimum of 3 years after the final study publication.

14.5 Protocol Deviations

Protocol deviations will be documented in a deviation log kept on the shared drive with all other study documents. Deviations will be reported to the IRB for review as required.

15 PUBLICATION POLICY

Following completion of the study, the investigator is expected to publish the results of this research in a scientific journal. The International Committee of Medical Journal Editors (ICMJE) member journals have adopted a trials-registration policy as a condition for publication. This policy requires that all clinical trials be registered in a public trials registry such as [ClinicalTrials.gov](#)*, which is sponsored by the National Library of Medicine. Other biomedical journals are considering adopting similar policies. For grants and cooperative agreements, it is the Institution's responsibility to register the trial in an acceptable registry. In addition, [NIH Public Access Policy](#) requires the principal investigator to submit journal articles that arise from NIH funds to the digital archive [PubMed Central](#).

The ICMJE defines a clinical trial as any research project that prospectively assigns human study participants to intervention or comparison groups to study the cause-and-effect relationship between a medical intervention and a health outcome. Studies designed for other purposes, such as to study pharmacokinetics or major toxicity (e.g., Phase I trials), would be exempt from registering trials in a public registry such as ClinicalTrials.gov.

SUPPLEMENTS/APPENDICES

Appendix A: Schedule of Events

APPENDIX A: SCHEDULE OF EVENTS

A detailed schematic describing all visits and assessments.

	Visit 1	Visit 2	Visit 3	Visit 4	Visit 5
Informed consent	X				
Documentation of current IBS-C symptoms via the IBS (GSRS-IBS)	X	X	X	X	X
Documentation of current laxative and/or antispasmodic use	X	X	X	X	X
Rectal Enema	X	X	X	X	X
Baseline 15 minutes	X	X	X	X	X
Experimental Protocol – Example of randomized TEA	ST36-100Hz	ST36-25Hz	PC6-100Hz	PC6-25Hz	Sham-TEA
Pregnancy Test (if participant is a woman with child bearing potential. If the woman is not on a birth control method)	X	X	X	X	X

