4.1 Schedule of Events for Each Visit

Every visit is the same and will follow the steps detailed below, with the exception of the first visit which will include the informed consent process. At visit one, the study team will randomly generate the stimulations schedule unique to each study participant; this is the order of locations and currents by using a random generator. For example, ST36-100Hz, ST36-25Hz, PC6-100Hz, PC6-25Hz and Sham-TEA.

48 Hours prior to the visit: The study participants will not take any medications known to affect the gut or pain perception.

8:00 pm on the night before the visit: The study participants begin fasting for their visit the next day. Study participants can still drink water. Study participants cannot drink coffee, tea, juices or eat any food items.

Day of the Visit:

Study participants will come to the study location, the Gastrointestinal Physiology Lab in University of Michigan. The visit will take place in one of the private rooms within the lab. **If the study participant is a women of child bearing potential:** She will complete a pregnancy test provided by the study team. If her pregnancy test is positive, she will be excluded from further participation in the study and will not complete the visit.

Rome IV Criteria for Irritable Bowel Syndrome: Upon arrival for every visit, the study participant will complete the Rome IV Criteria for Irritable Bowel Syndrome survey.

Enema: The study participant will be given a rectal enema to clean the rectum. Then the study participant will undress from the bottom down and be given a gown and sheets for comfort and privacy.

Position the study participant: The study participant will be asked to lie down on the medical examination table on one side and bring his or her knees up to the chest, similar to the fetal position. The table has rails that will protect the study participant from falling. The staff may use pillows to adjust and secure the study participant as well as for comfort.

Electrode Placement: The GI physiology laboratory staff will place two electrocardiogram (ECG) electrodes from of the TEA device on the subject's skin, one on the wrists at location PC6 and the other

Fig.1: Locations of PC6 and ST36.

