5.2 Study participant Exclusion Criteria

A potential study participant who meets any of the following exclusion criteria at baseline will be excluded from participation in this study if:

- Have an unrelated active disorder which may involve abdominal pain, such as inflammatory bowel disease, diabetes, unstable thyroid disease
- Have history of abdominal surgery other than cholecystectomy (gallbladder removal) or appendectomy
- Are taking anticoagulants or antispasmodic, antidiarrheal, or opioids or other pain relief medications and cannot stop these medications for three consecutive days before each study visit
- Are pregnant or breastfeeding; women of child bearing potential complete a pregnancy test at each visit
- Have known allergic reactions to components of the ECG electrodes
- Received treatment with an investigational drug or other intervention within 6 months of the date of consent
- Anything that, in the opinion of the investigator, would place the study participant at increased risk or preclude the study participant's full compliance with or completion of the study
- Are unable to provide informed consent

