7.2 Visit Schedule of Events

see section 4.1 Schedule of Events for Each Visit and Appendix A for a Table Describing the Schedule of Events

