9.2.4 Reporting of Pregnancy

If a study participant is pregnant she will be excluded from the study. If a study participant becomes pregnant during the study she will excluded from the remainder of the study.

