10.3 Final Analysis Plan

Analysis of variance (ANOVA) will be performed to investigate the difference in each of the outcomes among different sessions. Tukey's test will be used for study the differences in each of the measurements between two stimulation points (same stimulation parameters) and between two stimulation parameter sets (same stimulation points). The Pearson correlation analysis will also be performed to investigate the correlation between each of autonomic function parameters and the pain score or sensation threshold.

11 Source Documents and Access to Source Data/Documents

Only members of the study team will have access to source data. This includes: all information, original records of clinical findings, observations, or other activities in a clinical trial necessary for the reconstruction and evaluation of the trial.

12 Quality Control and Quality Assurance

- The study team will be present for each visit and follow the visit CRFs. The study team will go through the procedures with the GI physiology lab staff members to ensure that there is adherence to the protocol.
- The study team will sign the bottom of each study CRF at the end of the visit.

13 Ethics/Protection of Human Study participants

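### Appendix A exempts women on birth control from the pregnancy test that sections 4.1 and 5.2 require of every woman of child-bearing potential at each visit

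*Combined protocol and SAP*

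**What the plan says.** **Pregnancy test.** Section 4.1 opens with "Every visit is the same and will follow the steps detailed below", the only stated exception being consent at visit 1. For a woman of child-bearing potential it then states: "She will complete a pregnancy test provided by the study team". A positive result ends her participation. Section 5.2 repeats the rule within the exclusion criteria: "women of child bearing potential complete a pregnancy test at each visit". Neither section mentions contraception.

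The pregnancy row in Appendix A is marked for visits 1 to 5. Its label first restricts the test to women of child-bearing potential and then adds: "If the woman is not on a birth control method".

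Section 7.2 consists of one cross-reference: "see section 4.1 Schedule of Events for Each Visit and Appendix A for a Table Describing the Schedule of Events". It gives no order of precedence.

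On the consequence of pregnancy, section 9.2.4 says: "If a study participant becomes pregnant during the study she will excluded from the remainder of the study". Section 13.4 gives the safety of the woman and the fetus as the reason for excluding pregnant women.

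**DSMB.** Section 9.4 sets a first meeting one month after recruitment starts and a six-month interval from then to the end of the study, plus meetings triggered by an unexpected, possibly related SAE. Section 10.2.1 sets a three-month interval while enrolment and visits are under way, with more frequent meetings if needed.

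**Drug stop.** Section 4.1 instructs participants to take no gut-active or pain-active drugs from 48 hours before a visit. Section 5.2 excludes people on listed drug classes who cannot stop them for three days before each visit.

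**The concern.** The pregnancy test is the only step in the supplied text that would detect a pregnancy before the enema, rectal distension and stimulation. If staff apply the Appendix A row, a woman using contraception has no scheduled test at any visit, including the first. Her participation lasts 5 to 15 weeks. The exclusion in 5.2 and the removal in 9.2.4 would then depend on something the protocol does not describe.

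The conflict also affects conduct. Section 14.5 requires deviations to be logged and reported to the IRB as required. With two versions of the rule in force, staff cannot tell whether an untested contraceptive user is a deviation.

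The DSMB and drug-stop mismatches are of the same kind but matter less. The first leaves the routine review interval unclear during the months when participants are being exposed. The second means that participants are screened on a longer stop than they are later told to observe.

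**Working it through.** The plan gives no figure on these points to reproduce. The check is a comparison of texts with a little arithmetic.

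**1. Pregnancy test**

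| Source | Who is tested | When |
|---|---|---|
| Section 4.1 | Every woman of child-bearing potential | Every visit (all visits the same) |
| Section 5.2 | Every woman of child-bearing potential | Each visit |
| Appendix A | Women of child-bearing potential not on birth control | Visits 1 to 5 |

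For a woman of child-bearing potential not on birth control, all three agree: 5 visits × 1 test = 5 tests. For one on birth control, 4.1 and 5.2 give 5 × 1 = 5, and Appendix A gives 5 × 0 = 0. Testing her at every visit satisfies 4.1 and 5.2 and goes beyond Appendix A. Not testing her follows Appendix A and breaches 4.1 and 5.2. Section 7.2 names both 4.1 and Appendix A and ranks neither.

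**2. DSMB interval**

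The six-month rule in 9.4 begins straight after the month-1 meeting, so it covers the same enrolment and visit period as the three-month rule in 10.2.1. The two are not successive phases. They can still be met together. Section 10.2.1 gives no start for its cycle; if it is assumed to start at month 1, the first six-month date is 1 + 6 = 7 and the three-month cycle reaches it as 1 + 3 + 3 = 7. The same holds for each later six-month date while visits continue. A three-month schedule during visits, followed by a six-month one, therefore satisfies both sections. A six-month schedule alone does not satisfy 10.2.1.

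**3. Drug stop**

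Three days is 3 × 24 = 72 hours, and 72 − 48 = 24 hours. The classes that fall under both texts are opioids, other pain relief, antispasmodics and antidiarrheals. For these, the instruction is about one day per visit shorter than the period used for eligibility, or 5 × 1 = 5 days over five visits.

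**The case against.** **On pregnancy.** Sections 4.1 and 5.2 agree with each other, and Appendix A does not forbid testing, so staff who follow the body text breach nothing. The harm arises only if the appendix row is applied. That table omits the inflations, the VAS, the ECG and the Rome IV survey, so a visit cannot be run from it alone. Section 12 adds: "The study team will be present for each visit and follow the visit CRFs". Those forms are not in the documents and may carry the correct rule. One could also argue that the appendix clause was meant to define child-bearing potential, which the supplied text does not define.

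Much of this stands as a limit on the likely harm, but it does not remove the contradiction. Section 7.2 makes Appendix A a reference for visit procedures. The clause reads as a second condition added after child-bearing potential, and nothing in 4.1 or 5.2 supports reading it as a definition.

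**On the DSMB.** A reader might infer that the two sections cannot both be obeyed. They can, as shown above. SAE-triggered meetings and the halt to enrolment after serious adverse events do not depend on the routine interval.

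**On the drug stop.** A reader might infer that a dose taken between 48 and 72 hours before a visit breaches the protocol, or that it biases the comparison of sessions. Neither is supported. Section 5.2 tests ability to stop and 4.1 is the instruction, so someone able to stop for three days who stops for 48 hours complies with both. The primary outcome compares tolerance before and after TEA within one visit (3.2.1), and session order is randomized (5.4.1). A reader might also infer that 4.1 should instruct an anticoagulant hold because 5.2 lists that class. The documents do not establish this: 5.2 again concerns ability to stop, and a hold carries its own risk.

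**Conclusion.** The pregnancy conflict holds and is the main point. It is a contradiction in current text about a participant-safety rule: five scheduled tests or none for each contraceptive user of child-bearing potential. How many such women will enrol is not stated, and the documents do not show that any pregnancy would in fact be missed. The finding that no text ranks the versions is limited to the supplied pages; the visit forms were not available.

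The DSMB point holds in a smaller form. Two routine intervals are stated for the same period and should be made one, though they are compatible. The drug-stop point is minor: an instruction about 24 hours shorter than the eligibility period, with no breach of either section.

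None of the three changes the sample size, an error rate or the planned analysis.

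**What to change.** **Main change.** Delete the birth-control condition from the pregnancy row of Appendix A so that it matches 4.1 and 5.2, and check that the visit CRFs carry the same rule. The cost is up to five extra tests per affected woman.

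**Secondary.** State one DSMB schedule in both 9.4 and 10.2.1: month 1, then every three months during enrolment and visits, then every six months to study end, with SAE-triggered meetings unchanged. The cost is a few more meetings than 9.4 alone requires.

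**Minor.** In 4.1, lengthen the stop to three days for the gut-active and pain-active classes that 5.2 also lists, and leave 48 hours for other drugs covered by 4.1. The cost is about one more day off those drugs per visit for participants who use them.
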